### **8.1 Visit 1/Screening**

Visit 1 may be combined with Visit 2 but should be no more than 14 days following Visit 1. If visits are combined all procedures will be conducted at Visit 1.

Prior to the screening visit, telephone screening of interested subjects may be conducted using a telephone script. This will be conducted by the site recruitment staff or designee.

Screening procedures will be conducted by the Investigator, or suitably qualified designee.

The following procedures will be completed:

#### **8.1.1 Informed Consent**

The investigator, or designee, must obtain informed consent from each subject participating in this study after adequate explanation of the aims, methods, objectives, and potential hazards of the study. Two copies of the informed consent form (ICF) will be signed and dated by the subject, the subject will retain one copy and the other will be kept at site.

The investigator, or designee, must also explain to the subjects that they are completely free to refuse to enter the study or to withdraw from it at any time. Appropriate forms for documenting a signed and dated consent will be provided by either the investigator or by GSK CH.

The investigator, or designee, should sign and date each copy of the ICF to confirm that the consent process was completed correctly after the subject has signed.

The time the subject signed the informed consent form will also be captured on the Informed Consent Form as this is the point at which all Adverse Events will be captured from. The date and time of consent will be transcribed to the CRF.

If, during a subject's participation in the study, any new information becomes available that may affect the subject's willingness to participate in the study, each ongoing subject should receive a copy of this new information and be re-consented into the study. Each subject should be provided with a copy of the signed and dated amended consent form. The date of re-consent will be recorded on the CRF.

After signing the ICF, subjects will undergo the screening assessments to confirm that they meet all the inclusion criteria and none of the exclusion criteria. If the subject is confirmed eligible by the investigator (or designee) to participate in the study the subject is considered enrolled in the study.

### **8.1.2 Demographics**

The following demographic information will be recorded in the CRF: year of birth, gender and race. Fitzpatrick skin type assessment ([Appendix 3 - Fitzpatrick Skin Type Grading](#)) will also be conducted by a trained assessor and recorded on the CRF.

Race of subjects will be recorded in accordance with FDA Guidance for Industry: Collection of Race and Ethnicity Data in Clinical Trials, 2005.

### **8.1.3 Inclusion/Exclusion Criteria**

Subject compliance with all inclusion and exclusion criteria will be documented in the CRF.

### **8.1.4 Dermatologist Assessment**

A dermatologist will perform a visual assessment of the subject to confirm they are free of any pre-existing dermatological pathology at the screening visit.

This assessment will be repeated at Visit 2 (if not combined with visit 1) to ensure the subject remains free of any pre-existing dermatological pathology and that they are therefore suitable to continue in the study.

For each reaction score of '+' or greater during the challenge phase, a blinded dermatologist will further classify the reaction as potential sensitization (or not) and provide a narrative description of the event. The dermatologist will not be scoring the reaction. All practical efforts will be made to ensure the same dermatologist will be used to evaluate all subjects in the study.

Additionally, a final assessment at Visit 15 by a dermatologist will confirm it is medically appropriate to exit the subject from the study at the final visit. (Edward and Norman, 1982). The dermatologist may request further investigation as needed.

Confirmation of subject eligibility and continued eligibility will be documented in the CRF. Any subject narrative will also be documented in the CRF.

### **8.1.5 Medical History and Prior Medication/Treatment**

Details of relevant medical and surgical history (in the last 1 year), including allergies or drug sensitivity, will be documented in the CRF.

Prior medications/treatments, including prescription and non-prescription drugs, dietary supplements and herbal remedies, taken in the last 30 days and prior to signing the informed consent form, will be documented in the CRF.

### **8.1.6 Subject Eligibility**

The investigator and/or medically qualified designee will review inclusion/exclusion criteria, medical history, prior medications to confirm subject eligibility to participate in the clinical trial. This will be documented in the CRF.

To prepare for study participation, subjects will be instructed in the [Lifestyle Guidelines](#) and any [Current and Concomitant Medication/Treatment\(s\)](#) requirements of the protocol.

### **8.1.7 Randomization**

This assessment will be conducted at visit 2 (if not combined with visit 1).

Each subject will be assigned and identified by a unique Screening Subject Number. Any reference made to an individual subject within the study must be done using their unique Screening Subject Number. This will remain the same for each subject throughout the study duration.

All subjects who meet the criteria for entry into the study will be centrally randomized using Interactive Response Technology (IRT). Before the study is initiated, training, login information and directions for the IRT will be provided to the study site. Study products will be dispensed according to the instruction received through the IRT system at the appropriate study visits.

At visit 2, (or visit 1 if combined) a randomization number will be assigned electronically in ascending numerical order to each subject who is determined to be fully eligible. This randomization number will include the sites of application for each of the products into each cell for the induction phase. See also [5.4 Randomization Criteria](#) and [6.1.2 Preparation and Dispensing](#).

At visit 12 (challenge phase), another randomization number will be assigned electronically in ascending numerical order to each subject that completed the induction phase and meets the continued eligibility criteria. This randomization number will be different from the first one assigned at visit 2 (or visit 1) and will include the sites of application for each of the products into each cell for the challenge phase.

Randomization schedules for induction phase and challenge phase will follow respectively a 4x4 Latin Square (Williams) design.

The sequence of product application will remain the same within the subject for the induction phase, but a new sequence will be generated for each subject for the challenge phase.

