#### 4.3 Justification for Dose

A critical aspect of a patch test is that the whole test area of the cell is covered with the test product, without spreading or overlapping into other test sites (cells). Previous work has shown that the optimal dose to fulfil these requirements is 0.02 mL/cm^2 (Isaksson *et al*, 2007).

Therefore, in this study each of the test products will be dispensed at a dose of 0.02 mL/cm^2 into individual cells of a semi-occlusive adhesive patch system using an electronic pipette with disposable tips and applied to the designated area on the back. A sodium chloride (NaCl) saline solution (0.9%) will be used as a negative control product and dispensed at the same dose.

The semi-occlusive adhesive patches will be made of a hypoallergenic material and contain round cells of an absorbent material. One of the cells will contain the negative control and 3 other cells will be filled with each the test products according to the supplied randomization allocation for the induction and challenge phase. Only products of the sponsor, GSK CH, will be tested in this study.

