**Figure 5-1      Example of the semi-occlusive adhesive patch system (shown adhesive side down)**

The sequence of each of the study products to the cells within the patch system for each subject will be randomly assigned per the randomization sequence provided. The sequence of the products to the cells within each subject will remain the same for the induction phase, and a different sequence will be generated for each subject for the challenge phase. For more details on the randomization, please refer to [section 8.1.7](#)

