**Table 8-1 Application site sequences – induction phase**

An example of the randomization schedule for the induction phase is shown below:

Randomization Number	Induction phase			
	Cell A	Cell B	Cell C	Cell D
Patch Cell				
PPD	Test Product 1	Reference Product	Test Product 2	Test Product 3
	Test Product 3	Test Product 1	Reference Product	Test Product 2
	Test Product 2	Test Product 3	Test Product 1	Reference Product
	Reference Product	Test Product 2	Test Product 3	Test Product 1

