**Table 8-2 Application site sequences – challenge phase**

An example of the randomization schedule for the challenge phase is shown below:

Randomization Number	Challenge phase			
	Cell A	Cell B	Cell C	Cell D
Patch Cell				

Property of GSK Consumer Healthcare - Confidential

May not be used, divulged, published or otherwise disclosed without the consent of GSKCH  
 SP1963/SOP-208661: Template Version: 14 Mar 2019

PPD	Test Product 2	Test Product 3	Test Product 1	Reference Product
	Reference Product	Test Product 1	Test Product 3	Test Product 2
	Test Product 3	Reference Product	Test Product 2	Test Product 1
	Test Product 1	Test Product 2	Reference Product	Test Product 3

## 8.2 Study Period – Baseline to Visit 14

Visit 2 may be combined with Visit 1 (Screening) but should be no more than 14 days following Visit 1.

During the study period subjects should be reminded to inform the site if they experience any untoward medical occurrence or if they use any new medications or treatments and report at their next visit.

### 8.2.1 Visit 2/Day 1

Changes in concomitant medication or non-drug treatments/procedures will be documented in the CRF.

Spontaneous reporting of AEs and those elicited by asking subjects to respond to a non-leading question such as “How do you feel?” will be assessed and any AEs recorded in the CRF.

A qualified dermatologist will check for subject continued eligibility in the study (at Visit 2 only if Visits are not combined).

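### Does it matter that the example induction square (Protocol Table 8-1) is cyclic rather than Williams and shares a row with Table 8-2?

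*Protocol*

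**What the plan says.** Protocol 8.1.7 gives the rule for both phases: "Randomization schedules for induction phase and challenge phase will follow respectively a 4x4 Latin Square (Williams) design". Two tables follow. Table 8-1 is introduced with "An example of the randomization schedule for the induction phase is shown below" and Table 8-2 with "An example of the randomization schedule for the challenge phase is shown below". Their randomization numbers are redacted.

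The first row of Table 8-1, cells A to D, reads "Test Product 1 Reference Product Test Product 2 Test Product 3" and its third row reads "Test Product 2 Test Product 3 Test Product 1 Reference Product". The first row of Table 8-2 holds the same order as that third row.

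On the change between phases, Protocol 5.4 says that "a different sequence will be generated for each subject for the challenge phase". Section 8.1.7 adds that the randomization number issued at Visit 12 differs from the one issued at Visit 2, and that numbers are given out in ascending order to subjects who completed induction and remain eligible. It states no rule tying a subject's challenge order to that subject's induction order.

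The operative schedule is generated by a vendor with validated software (Protocol 6.1.2) and issued through the IRT (Protocol 6.5). SAP 1.1 repeats that the challenge sequence differs and does not mention the Williams design.

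**The concern.** A Williams square is chosen over a plain Latin square for one reason: it places every product next to every other product equally often. If the printed induction square is only cyclic, that property is absent from the phase with nine applications to the same site.

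Protocol 4.3 treats containment of each product within its own cell as critical. If product did migrate, or a strong reaction spread, an unbalanced layout would expose saline to some test products and never to others. Saline is the reference against which the sponsor will read the test products (Protocol 4.1), so a neighbour effect would be mixed up with product.

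The shared row raises a second doubt. The protocol promises a different sequence at challenge, yet only the randomization number is explicitly made to differ. On the printed rows, a subject given the third induction row could draw the same order again at challenge.

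**Working it through.** The plan gives no numerical figure here. The claim to check is the design label, and the inputs are the rows of Tables 8-1 and 8-2 (T1 to T3 are the test products, Ref is saline).

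| Row | Table 8-1, cells A-D | Table 8-2, cells A-D |
|---|---|---|
| 1 | T1, Ref, T2, T3 | T2, T3, T1, Ref |
| 2 | T3, T1, Ref, T2 | Ref, T1, T3, T2 |
| 3 | T2, T3, T1, Ref | T3, Ref, T2, T1 |
| 4 | Ref, T2, T3, T1 | T1, T2, Ref, T3 |

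**Latin property.** In both squares each product appears once per row and once per cell, so position is balanced in both phases.

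**Williams property.** Four products give 4 × 3 = 12 ordered neighbour pairs. Four rows give 4 × 3 = 12 left-to-right neighbours, so a Williams square holds each pair once.

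- Table 8-1: T1-Ref, Ref-T2, T2-T3 and T3-T1 occur three times each (4 × 3 = 12) and the other eight never. It is cyclic, not Williams.
- Table 8-2: all 12 pairs occur once. It is Williams.

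**Overlap.** Of 4 × 4 = 16 row pairings, one matches: induction row 3 with challenge row 1. Read line against line (1-1, 2-2, 3-3, 4-4), none match. Assuming the real lists used exactly these rows, with equal frequency and independent draws, the chance of a repeat is 1/4 × 1/4 = 1/16 = 6.25%. That is 280/16 = 17.5 randomized subjects, or 200/16 = 12.5 evaluable subjects. It is zero if the IRT blocks that one pairing.

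**Does the neighbour count describe real neighbours?** Only if cells A to D lie in a line. The patch has six cells, and the layout figure is not available. The table counts the rows, out of four, in which saline shares a side with each test product under two layouts. The alternative square is one that is Williams and shares no row with Table 8-2: (T1, Ref, T3, T2), (Ref, T2, T1, T3), (T2, T3, Ref, T1), (T3, T1, T2, Ref).

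| Square | In line: T1, T2, T3 | Block AB over CD: T1, T2, T3 |
|---|---|---|
| Table 8-1 (cyclic) | 3, 3, 0 | 2, 2, 4 |
| Table 8-2 (Williams) | 2, 2, 2 | 4, 0, 4 |
| Alternative (Williams) | 2, 2, 2 | 4, 4, 0 |

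In a line, the cyclic square never puts saline beside Product 3. In a block it does so in every row, and both Williams squares leave one product out altogether. The Williams label secures neighbour balance in a line and nowhere else.

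**The case for a change.** The strongest case for a change is that an example of a Williams schedule ought to be one. Table 8-2 gets it right, Table 8-1 is the only induction schedule shown, and the SAP is silent, so a reader cannot tell whether text or table governs the list. Correcting it before the first randomization would cost almost nothing. Nor can line-by-line pairing be relied on to prevent repeats, because challenge numbers go only to subjects who reach Visit 12, and any dropout shifts the alignment.

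The factual part of this stands: the induction label and the example disagree, and the text states no mechanism that excludes a subject's own induction order. The inference that the trial is affected does not. The sentence in 8.1.7 states the requirement and the tables illustrate it, so whoever builds the list has the rule in words, both for the design and for the change of sequence. SAP 4.3 plans a listing of planned and actual product by cell and phase, so the allocation actually used will be open to inspection.

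It is also too much to say that both promises fail. The challenge example is a proper Williams square. The different-sequence rule applies within a subject, and a row common to two lists does not break it.

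**Conclusion.** No change to the plan follows. Table 8-1 is a mislabelled example, and the missing IRT constraint is a detail that the list builder can settle from the text as it stands.

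The effect on results is negligible for four reasons.

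- Position is balanced in both printed squares, so no product is tied to a particular cell.
- The primary endpoint is the dermatologist's classification of challenge-phase reactions (SAP 4.4.1.1), where the printed square is Williams. An induction neighbour effect would bear directly only on the induction irritation scores, which belong to the secondary endpoint.
- The analysis is proportions with Clopper-Pearson intervals by product. SAP 4.4.1.2 plans no formal statistical analysis for the primary endpoint, and no analysis carries a position or neighbour term. No stated figure would move.
- Protocol 4.3 gives containment within the cell as the reason for the amount dispensed, so the spread that neighbour balance guards against is already addressed by design.

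A repeated sequence in up to about 1 in 16 subjects would also do little harm. It requires exactly the printed rows and independent draws. The evaluator and dermatologist do not know the order in either phase, so a repeat tells them nothing, and the challenge patch goes on previously unpatched skin.

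The one point that could matter is neighbour balance for saline during induction. It rests on an in-line layout that the available text does not establish. Under a block layout, substituting a Williams square could remove the contact between saline and Product 3 that the cyclic square provides, so a gain from changing the square is not shown.

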**Table 8-1 Application site sequences – induction phase**

An example of the randomization schedule for the induction phase is shown below:

Randomization Number	Induction phase			
	Cell A	Cell B	Cell C	Cell D
Patch Cell				
PPD	Test Product 1	Reference Product	Test Product 2	Test Product 3
	Test Product 3	Test Product 1	Reference Product	Test Product 2
	Test Product 2	Test Product 3	Test Product 1	Reference Product
	Reference Product	Test Product 2	Test Product 3	Test Product 1

**Table 8-2 Application site sequences – challenge phase**

An example of the randomization schedule for the challenge phase is shown below:

Randomization Number	Challenge phase			
	Cell A	Cell B	Cell C	Cell D
Patch Cell				

Property of GSK Consumer Healthcare - Confidential

May not be used, divulged, published or otherwise disclosed without the consent of GSKCH  
 SP1963/SOP-208661: Template Version: 14 Mar 2019

PPD	Test Product 2	Test Product 3	Test Product 1	Reference Product
	Reference Product	Test Product 1	Test Product 3	Test Product 2
	Test Product 3	Reference Product	Test Product 2	Test Product 1
	Test Product 1	Test Product 2	Reference Product	Test Product 3

## 8.2 Study Period – Baseline to Visit 14

Visit 2 may be combined with Visit 1 (Screening) but should be no more than 14 days following Visit 1.

During the study period subjects should be reminded to inform the site if they experience any untoward medical occurrence or if they use any new medications or treatments and report at their next visit.

### 8.2.1 Visit 2/Day 1

Changes in concomitant medication or non-drug treatments/procedures will be documented in the CRF.

Spontaneous reporting of AEs and those elicited by asking subjects to respond to a non-leading question such as “How do you feel?” will be assessed and any AEs recorded in the CRF.

A qualified dermatologist will check for subject continued eligibility in the study (at Visit 2 only if Visits are not combined).

#### 8.2.1.1 Baseline Grading

Visit 2/Day 1 (or Visit 1 if visits combined), the induction phase; the test area for the application of the adhesive patch will be designated between the scapula and waistline and away from the spinal mid-line. Baseline assessment of the application test sites will then be performed by a blinded trained evaluator per the assessment scale in [Appendix 2](#).

Baseline assessment scores will be documented in the CRF.

#### 8.2.1.2 Patch (Product) Application

The study will progress in 3-phases, as follows:

##### Induction Phase:

A semi-occlusive adhesive patch with 6 cells labelled A-F will be used. Four cells (A-D) will be used in this study (1 for each test product and 1 for the saline solution). Two cells (E-F) will remain empty. See also [5.4 Randomization Criteria](#) and [6.1.2 Preparation and Dispensing](#).

A controlled amount (0.02 mL/cm^2) of each study product will be dispensed using suitable measuring apparatus (e.g. a pipette) into the appropriate separate cell, 3 cells for each of the test products and 1 cell for the saline solution. The assignment of the study products to the cells within the patch system within each subject will be randomly assigned per the randomization schedule provided. The sequence of the products to the cells for each subject will remain the same for the induction phase, and a different sequence per the randomization provided will be

generated for each subject for the challenge phase. The adhesive patch will then be applied to the dorsum of the subject.

During the induction phase there will be a total of 9 patch applications over 3 consecutive weeks, with patches applied on alternate weekdays each week (Monday, Wednesday, and Friday).

Each patch will remain in place for 48 ( $\pm 4$ ) hours on weekdays and 72 ( $\pm 4$ ) hours on weekends. The patch will then be removed, and the area may be gently wiped with saline solution. Subjects will be instructed to rest for 15-30 minutes (maximum 1 hour) in standard room conditions (18-26°C) avoiding contact of the back area with any other surface. After 30 minutes (maximum of 1 hour), the test sites will be evaluated as per the scale in [Appendix 2](#). Assessment scores will be documented in the CRF.

A new adhesive patch with each of the products applied to the same cells will then be applied to the same area on the dorsum.

**Rest Phase:**

At visit 11, after the final induction patch removal and evaluation, subjects will enter a minimum 2-week rest phase. During this time there will be no product or patch applications. Subjects will be reminded to continue to follow the [Lifestyle Considerations](#) throughout the rest phase

**Challenge Phase:**

At visit 12, after completing the rest phase, subjects will return for the challenge phase. A naïve (i.e. previously untreated/patched) area of skin on the back, between the shoulder line and waist and away from the spinal mid-line, will be selected for the challenge patch. This area will be evaluated by the blinded evaluator prior to any patch application to provide a baseline for interpretation. A new patch, with each of the cells filled with study products as per the randomization sequence for the subject's challenge phase, will then be applied.

After 48 ( $\pm 4$ ) hours, subjects will return to the site, the patch will be removed, and the area may be gently wiped with saline solution. Subjects will be instructed to rest for 15-30 minutes (maximum 1 hour) in standard room conditions (18-26°C) avoiding contact of the back area with any other surface. After 30 minutes (maximum of 1 hour), the test sites will be evaluated as per the scale in [Appendix 2](#). Subjects will return to site for subsequent test-site evaluations 24 ( $\pm 4$ ) hours - Visit 13 and 48 ( $\pm 4$ ) hours - Visit 14 post patch removal as per the scale in [Appendix 2](#). Assessment scores will be documented in the CRF.

